APPENDIX 2. PROHIBITED CONCOMITANT MEDICATIONS AND PROCEDURES

The following concomitant medications and procedures are prohibited prior to randomization and during the course of the study unless otherwise specified.

1. Topical therapy:

Topical therapy unless otherwise specified (including but not limited to topical corticosteroids, topical retinoid [tazarotene] or vitamin D analogue preparations [calcipotriene and calcitriol], tacrolimus, pimecrolimus, methoxsalen, trimethylpsoralen, pimecrolimus or anthralin/dithranol). Topical therapy is prohibited from 2 weeks prior to the first administration of study treatment until 4 weeks after the last dose of study treatment unless otherwise specified in [Section 9.6.1](#).

2. Systemic therapy:

Systemic therapy including but not limited to oral or injectable retinoids, apremilast (or any other PDE4 inhibitors), acitretin, methotrexate, cyclosporine, corticosteroids, mycophenolate mofetil, 6-thioguanine, hydroxyurea, thioguanine, sirolimus, isotretinoin, sulfasalazine, azathioprine, or fumaric acid esters are be prohibited from 4 weeks prior to the first administration of study treatment until 4 weeks after the last dose of study treatment.

CCI

3. Biologic Agents:

- Tumor necrosis factor (TNF)- α inhibitors (certolizumab pegol, etanercept, adalimumab, infliximab, and golimumab) are prohibited from 8 weeks prior to the first administration of study treatment until 4 weeks after the last dose of study treatment.
- TNF- α inhibitor, rituximab, is prohibited from 24 weeks prior to the first administration of study treatment until 4 weeks after the last dose of study treatment.
- Interleukin (IL)-12/23 inhibitors (ustekinumab or any other therapeutic agent targeting IL-12 or IL-23) is prohibited from 24 weeks prior to the first administration of study treatment until 4 weeks after the last dose of study treatment.
- IL-17 inhibitors (secukinumab, ixekizumab, brodalumab, or any other therapeutic agent targeting IL-17) are prohibited from 24 weeks prior to the first administration of study treatment until 4 weeks after the last dose of study treatment.

- IL-23 inhibitors (tildrakizumab, risankizumab, guselkumab, or any other therapeutic agent targeting IL-23) are prohibited from 24 weeks prior to the first administration of study treatment until 4 weeks after the last dose of study treatment.
- IL-12 inhibitors (briakinumab or any other therapeutic agent targeting IL-12) are prohibited from 24 weeks prior to the first administration of study treatment until 4 weeks after the last dose of study treatment.
- T-cell inhibitors: alemtuzumab, abatacept, alefacept - from 12 weeks prior to the first administration of study treatment until 4 weeks after the last dose of study treatment.
- Integrin receptor antagonist: natalizumab - from 12 weeks prior to the first administration of study treatment until 4 weeks after the last dose of study treatment.

4. Phototherapy:

Prolonged exposure to ultraviolet B (including narrow band ultraviolet B, Goeckerman therapy and excimer laser) or psoralen ultraviolet A unless otherwise specified in [Section 8.2](#) and [Section 9.6.1](#). Phototherapy is prohibited from 4 weeks prior to the first administration of study treatment until 4 weeks after the last dose of study treatment.

5. Use of any investigational drug:

Investigational drugs for biologic therapy are prohibited from 24 weeks prior to Day 1 until 4 weeks after the last dose of study treatment. All non-biologic investigational drugs/therapy/devices are prohibited from 4 weeks (or 5 half-lives whichever is longer) prior to Day 1 until after the last dose of study treatment.

6. Prolonged sun exposure or use of artificial sunbathing (eg, tanning booths) or other UV light sources from Day 1 until after the last dose of study treatment (ie, Treatment Period).
7. Subject has had a recent initiation of a drug that is known to potentially cause or exacerbate psoriasis (including, but not limited to, beta blockers, lithium, and anti-malarials), within the 8 weeks prior to the first administration of study treatment; a those subject who have has been on a stable dose for at least 8 weeks prior to the first administration of study treatment without exacerbation of psoriasis may be enrolled randomized and does not need to discontinue these medications.

APPENDIX 3. PSORIASIS AREA SEVERITY INDEX - WORKSHEET

The Psoriasis Area and Severity Index (PASI) is a quantitative rating score for measuring the severity of psoriatic lesions based on area coverage and plaque appearance.

Plaque characteristic	Lesion score	Head	Upper Limbs	Trunk	Lower Limbs
Erythema	0 = None				
	1 = Slight				
Induration/Thickness	2 = Moderate				
	3 = Severe				
Scaling	4 = Very severe				
Add together each of the 3 scores for each body region to give 4 separate sums (A).					
Lesion Score Sum (A)					

Percentage area affected	Area score	Head	Upper Limbs	Trunk	Lower Limbs
Area Score (B) Degree of involvement as a percentage for each body region affected (score each region with score between 0-6)	0 = 0% 1 = 1% - 9% 2 = 10% - 29% 3 = 30% - 49% 4 = 50% - 69% 5 = 70% - 89% 6 = 90% - 100%				
Multiply Lesion Score Sum (A) by Area Score (B), for each body region, to give 4 individual subtotals (C).					
Subtotals (C)					
Multiply each of the Subtotals (C) by amount of body surface area represented by that region, i.e. x 0.1 for head, x 0.2 for upper body, x 0.3 for trunk, and x 0.4 for lower limbs.					
Body Surface Area		x 0.1	x 0.2	x 0.3	x 0.4
Totals (D)					
Add together each of the scores for each body region to give the final PASI Score.					

PASI Score =

Reference

1. British Association of Dermatologists. Accessed at <http://www.bad.org.uk/shared/get-file.ashx?id=1654&itemtype=document>. Accessed on 05 Oct 2021.

APPENDIX 4. 5-POINT STATIC PHYSICIAN'S GLOBAL ASSESSMENT

For the determination of Static Physician's Global Assessment (sPGA), the degree of overall lesion severity will be evaluated using the categories below:

- 0 = Clear: No signs of psoriasis. Post-inflammatory hyperpigmentation may be present
- 1 = Almost clear: Normal to pink coloration of lesions; no thickening; no to minimal focal scaling.
- 2 = Mild: Pink to light red coloration; just detectable to mild thickening; predominantly fine scaling
- 3= Moderate: Dull bright red, clearly distinguishable erythema; clearly distinguishable to moderate thickening; moderate scaling
- 4 = Severe: Bright to deep dark red coloration; severe thickening with hard edges; severe/coarse scaling covering almost all or all lesions

Reference

APPENDIX 5. DERMATOLOGY LIFE QUALITY INDEX

The aim of this questionnaire is to measure how much your skin problem has affected your life OVER THE LAST WEEK. Please tick (✓) one box for each question.

1. Over the last week, how itchy, sore, painful or stinging has your skin been?	Very much  A lot  A little  Not at all 
2. Over the last week, how embarrassed or self-conscious have you been because of your skin?	Very much  A lot  A little  Not at all 
3. Over the last week, how much has your skin interfered with you going shopping or looking after your home or garden?	Very much  A lot  A little  Not at all  Not relevant 
4. Over the last week, how much has your skin influenced the clothes you wear?	Very much  A lot  A little  Not at all  Not relevant 
5. Over the last week, how much has your skin affected any social or leisure activities?	Very much  A lot  A little  Not at all  Not relevant 
6. Over the last week, how much has your skin made it difficult for you to do any sport?	Very much  A lot  A little  Not at all  Not relevant 
7. Over the last week, has your skin prevented you from working or studying?	Yes  No  Not Relevant 
If "No", over the last week how much has your skin been a problem at work or studying?	A lot  A little  Not at all 
8. Over the last week, how much has your skin created problems with your partner or any of your close friends or relatives?	Very much  A lot  A little  Not at all  Not relevant 

9. Over the last week, how much has your skin caused any sexual difficulties ?	Very much	
	A lot	
	A little	
	Not at all	
	Not relevant	
10. Over the last week, how much of a problem has the treatment for your skin been, for example, by making your home messy, or by taking up time?	Very much	
	A lot	
	A little	
	Not at all	
	Not relevant	

Please check you have answered EVERY question. Thank you.

Reference

APPENDIX 6.

COLUMBIA-SUICIDE SEVERITY RATING SCALE
(Screening Version)

SUICIDAL IDEATION		Past X Months

Ask questions 1 and 2. If both are negative, proceed to "Suicidal Behavior" section. If the answer to question 2 is "yes", ask questions 3, 4 and 5. If the answer to question 1 and/or 2 is "yes", complete "Intensity of Ideation" section below.
		

1. Wish to be Dead Subject endorses thoughts about a wish to be dead or not alive anymore, or wish to fall asleep and not wake up. Have you wished you were dead or wished you could go to sleep and not wake up?
 
If yes, describe:
		Yes No  

2. Non-Specific Active Suicidal Thoughts General, non-specific thoughts of wanting to end one's life/commit suicide (e.g., "I've thought about killing myself") without thoughts of ways to kill oneself/associated methods, intent, or plan. Have you actually had any thoughts of killing yourself?
 
If yes, describe:
		Yes No  

3. Active Suicidal Ideation with Any Methods (Not Plan) without Intent to Act Subject endorses thoughts of suicide and has thought of at least one method during the assessment period. This is different than a specific plan with time, place or method details worked out (e.g., thought of method to kill self but not a specific plan). Includes person who would say, "I thought about taking an overdose but I never made a specific plan as to when, where or how I would actually do it....and I would never go through with it." Have you been thinking about how you might do this?
 
If yes, describe:
		Yes No  

4. Active Suicidal Ideation with Some Intent to Act, without Specific Plan Active suicidal thoughts of killing oneself and subject reports having some intent to act on such thoughts, as opposed to "I have the thoughts but I definitely will not do anything about them." Have you had these thoughts and had some intention of acting on them?
 
If yes, describe:
		Yes No  

5. Active Suicidal Ideation with Specific Plan and Intent Thoughts of killing oneself with details of plan fully or partially worked out and subject has some intent to carry it out. Have you started to work out or worked out the details of how to kill yourself? Do you intend to carry out this plan?
 
If yes, describe:
		Yes No  
INTENSITY OF IDEATION		

The following features should be rated with respect to the most severe type of ideation (i.e., 1-5, from above, with 1 being the least severe and 5 being the most severe). Ask about time he/she was feeling the most suicidal.
 
Most Severe Ideation:
		Most Severe

Type # (1-5)
		Description of Ideation

Frequency How many times have you had these thoughts? (1) Less than once a week (2) Once a week (3) 2-5 times in week (4) Daily or almost daily (5) Many times each day
		—

Duration When you have the thoughts, how long do they last? (1) Fleeting - few seconds or minutes (4) 4-8 hours/most of day (2) Less than 1 hour/some of the time (5) More than 8 hours/persistent or continuous (3) 1-4 hours/a lot of time
		—

Controllability Could/can you stop thinking about killing yourself or wanting to die if you want to? (1) Easily able to control thoughts (4) Can control thoughts with a lot of difficulty (2) Can control thoughts with little difficulty (5) Unable to control thoughts (3) Can control thoughts with some difficulty (6) Does not attempt to control thoughts
		—

Deterrents Are there things - anyone or anything (e.g., family, religion, pain of death) - that stopped you from wanting to die or acting on thoughts of committing suicide? (1) Deterrents definitely stopped you from attempting suicide (4) Deterrents most likely did not stop you (2) Deterrents probably stopped you (5) Deterrents definitely did not stop you (3) Uncertain that deterrents stopped you (6) Does not apply
		—

Reasons for Ideation What sort of reasons did you have for thinking about wanting to die or killing yourself? Was it to end the pain or stop the way you were feeling (in other words you couldn't go on living with this pain or how you were feeling) or was it to get attention, revenge or a reaction from others? Or both? (1) Completely to get attention, revenge or a reaction from others (4) Mostly to end or stop the pain (you couldn't go on living with the pain or how you were feeling) (2) Mostly to get attention, revenge or a reaction from others (5) Completely to end or stop the pain (you couldn't go on living with the pain or how you were feeling) (3) Equally to get attention, revenge or a reaction from others and to end/stop the pain (6) Does not apply
		—

SUICIDAL BEHAVIOR (Check all that apply, so long as these are separate events; must ask about all types)		Past X Years or Lifetime	

Actual Attempt: A potentially self-injurious act committed with at least some wish to die, as a result of act. Behavior was in part thought of as method to kill oneself. Intent does not have to be 100%. If there is any intent desire to die associated with the act, then it can be considered an actual suicide attempt. There does not have to be any injury or harm, just the potential for injury or harm. If person pulls trigger while gun is in mouth but gun is broken so no injury results, this is considered an attempt.
 
Inferring Intent: Even if an individual denies intent/wish to die, it may be inferred clinically from the behavior or circumstances. For example, a highly lethal act that is clearly not an accident so no other intent but suicide can be inferred (e.g., gunshot to head, jumping from window of a high floor/story). Also, if someone denies intent to die, but they thought that what they did could be lethal, intent may be inferred.
 
Have you made a suicide attempt?
 
Have you done anything to harm yourself?
 
Have you done anything dangerous where you could have died?
 
What did you do?
 
Did you _____ as a way to end your life?
 
Did you want to die (even a little) when you _____?
 
Were you trying to end your life when you _____?
 
Or did you think it was possible you could have died from _____?
 
Or did you do it purely for other reasons / without ANY intention of killing yourself (like to relieve stress, feel better, get sympathy, or get something else to happen)? (Self-injurious Behavior without suicidal intent)
 
If yes, describe: _____
		
Yes  No 
 
—
 
Total # of Attempts
 
—
	

Has subject engaged in Non-Suicidal Self-Injurious Behavior?
 
Interrupted Attempt: When the person is interrupted (by an outside circumstance) from starting the potentially self-injurious act (if not for that, actual attempt would have occurred).
 
Overdose: Person has pills in hand but is stopped from ingesting. Once they ingest any pills, this becomes an attempt rather than an interrupted attempt.
 
Shooting: Person has gun pointed toward self, gun is taken away by someone else, or is somehow prevented from pulling trigger. Once they pull the trigger, even if the gun fails to fire, it is an attempt.
 
Jumping: Person is poised to jump, is grabbed and taken down from ledge.
 
Hanging: Person has noose around neck but has not yet started to hang - is stopped from doing so.
 
Has there been a time when you started to do something to end your life but someone or something stopped you before you actually did anything?
 
If yes, describe: _____
		
Yes  No 
 
—
 
Yes  No 
 
—
 
Total # of interrupted
 
—
	

Aborted Attempt: When person begins to take steps toward making a suicide attempt, but stops themselves before they actually have engaged in any self-destructive behavior. Examples are similar to interrupted attempts, except that the individual stops him/herself, instead of being stopped by something else.
 
Has there been a time when you started to do something to try to end your life but you stopped yourself before you actually did anything?
 
If yes, describe: _____
		
Yes  No 
 
—
 
Total # of aborted
 
—
	

Preparatory Acts or Behavior:
 
Acts or preparation towards immediately making a suicide attempt. This can include anything beyond a verbalization or thought, such as assembling a specific method (e.g., buying pills, purchasing a gun) or preparing for one's death by suicide (e.g., giving things away, writing a suicide note).
 
Has you taken any steps towards making a suicide attempt or preparing to kill yourself (such as collecting pills, getting a gun, giving valuables away or writing a suicide note)?
 
If yes, describe: _____
		
Yes  No 
 
—
	

Suicidal Behavior:
 
Suicidal behavior was present during the assessment period?
		
Yes  No 
 
—
	

Answer for Actual Attempts Only
		Most Recent Attempt Date:	Most Lethal Attempt Date:

Actual Lethality/Medical Damage:
 
0. No physical damage or very minor physical damage (e.g., surface scratches).
 
1. Minor physical damage (e.g., lethargic speech; first-degree burns; mild bleeding; sprains).
 
2. Moderate physical damage; medical attention needed (e.g., conscious but sleepy; somewhat responsive; second-degree burns; bleeding of major vessel).
 
3. Moderately severe physical damage; medical hospitalization and likely intensive care required (e.g., comatose with reflexes intact; third-degree burns less than 20% of body; extensive blood loss but can recover; major fractures).
 
4. Severe physical damage; medical hospitalization with intensive care required (e.g., comatose without reflexes; third-degree burns over 20% of body; extensive blood loss with unstable vital signs; major damage to a vital area).
 
5. Death
		Enter Code	Enter Code

Potential Lethality: Only Answer if Actual Lethality=0
 
Likely lethality of actual attempt if no medical damage (the following examples, while having no actual medical damage, had potential for very serious lethality: put gun in mouth and pulled the trigger but gun fails to fire so no medical damage; laying on train tracks with oncoming train but pulled away before run over).
 
0 = Behavior not likely to result in injury
 
1 = Behavior likely to result in injury but not likely to cause death
 
2 = Behavior likely to result in death despite available medical care
		Enter Code	Enter Code

Reference

## Revision History

Version #	Date (DD-Mmm-YYYY)	Document Owner	Revision Summary
v0.1	18-Mar-2022	PPD	Initial Release Version
v0.2	19-Apr-2022		Revised draft addressing sponsor comments.
v1.0	13-Jun-2022		Finalized version.
v1.1	07-Jun-2023		Updated version with the following main updates: - screened set and randomized set are added in the analysis sets; clarifications are provided regarding defining safety analysis sets in the event of drug mis-dispensation; pharmacokinetic set and CCI [REDACTED] are updated to account for drug mis-dispensation. - estimands are updated for secondary efficacy points to allow for imputation (LOCF and NRI) for sPGA related secondary endpoint. - imputation rules for missing start dates are updated - additional analyses are added in the section of secondary efficacy endpoints and analysis - additional analysis of TEAEs by time of onset is added - additional outputs are added in the Index of Tables
v2.0	26-Jun-2023		Finalized version.
v3.0	11-Jul-2023		Finalized version.

This document is confidential.

I confirm that I have reviewed this document and agree with the content.

Approvals		
PPD	Approval	
PPD	PPD	Jul 11, 2023
Name, Title Lead Biostatistician	Signature	Date (DD-Mmm-YYYY)
PPD	PPD	Jul 11, 2023
Name, Title Pharmacokineticist	Signature	Date (DD-Mmm-YYYY)
PPD	PPD	Jul 11, 2023
Name, Title Senior Reviewing Biostatistician	Signature	Date (DD-Mmm-YYYY)
Meiji Pharma USA Inc. Approval		
PPD	PPD	Jul 12, 2023
Name, Title Sponsor Contact	Signature	Date (DD-Mmm-YYYY)

This document is confidential.

## 1. Glossary of Abbreviations

Abbreviation	Description
AE	Adverse Event
AIC	Akaike's Information Criteria
ATC	Anatomical Therapeutic Chemical
BDRM	Blind Data Review Meeting
BID	Twice Daily
BLQ	Below the Limit of Quantification
BMI	Body Mass Index
BSA	Body Surface Area
CI	Confidence Interval
CMH	Cochran-Mantel-Haenszel
CS	Clinically Significant
C-SSRS	Columbia-Suicide Severity Rating Scale
CTMS	Clinical Trial Management System
C trough	Trough Plasma Concentration
CV	Coefficient of Variation
DLQI	Dermatology Life Quality Index
ECG	Electrocardiogram
eCRF	Electronic Case Report Form
FAS	Full Analysis Set
FSH	Follicle-Stimulating Hormone
GCP	Good Clinical Practice
GI	Gastrointestinal
HBV	Hepatitis B Virus
HCV	Hepatitis C Virus
HIV	Human Immunodeficiency Virus
IB	Investigator's Brochure
ICF	Informed Consent Form
ICH	International Council for Harmonisation
ID	Subject Identification

This document is confidential.

Abbreviation	Description
IL	Interleukin
IWRS	Interactive Web Response System
LLT	Lower Level Term
LOCF	Last Observation Carried Forward
LS	Least-square
MedDRA	Medical Dictionary for Regulatory Activities
MMRM	Mixed-effect Model for Repeated Measures
NRI	Non-responder Imputation
NRS	Numerical Rating Scale
PASI	Psoriasis Area and Severity Index
PASI-50	≥ 50% Reduction from Baseline in the PASI score
PASI-75	≥ 75% Reduction from Baseline in the PASI score
PASI-90	≥ 90% Reduction from Baseline in the PASI score
PASI-100	100% Reduction from Baseline in the PASI score
CCI	
PDE4	Phosphodiesterase 4
PK	Pharmacokinetic
PP	Patient Privacy
PPS	Per Protocol Set
PRO	Patient-reported Outcome
PT	Preferred Term
QD	Once Daily
QTc	Corrected QT Interval
QTcF	QT Interval Corrected using Fridericia's Formula
REML	Restricted Maximum Likelihood
SAE	Serious Adverse Event
SAP	Statistical Analysis Plan
SD	Standard Deviation
SOC	System Organ Class
SOP	Standard Operating Procedure
sPGA	Static Physician's Global Assessment

This document is confidential.

Abbreviation	Description
TEAE	Treatment-Emergent Adverse Event
TFL	Tables, Figures and Listings
TNF- $\alpha$	Tumor Necrosis Factor-alpha
UV	Ultraviolet
UVB	Ultraviolet B
WHO	World Health Organization
WOCBP	Women of Childbearing Potential

This document is confidential.

## **2. Purpose**

The purpose of this statistical analysis plan (SAP) is to ensure that the data listings, summary tables and figures which will be produced, and the statistical methodologies which will be used, are complete and appropriate to allow valid conclusions regarding the study objectives.

### **2.1. Responsibilities**

PPD [REDACTED] will perform the statistical analyses and is responsible for the production and quality control of all tables, figures, and listings.

### **2.2. Timings of Analyses**

The primary analysis of safety, efficacy and pharmacokinetics [REDACTED] CCI [REDACTED] is planned after all subjects complete the final study visit (Visit 8 at Week 16) or terminate early from the study. Database will be completely cleaned and locked prior to the primary analysis. No interim analyses are planned for the study.

This document is confidential.

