7.3 End of Study

A subject will have fulfilled the requirements for study completion if/when the subject has completed all study periods (ie, Screening Period, Treatment Period, and Follow-up Period) as indicated in the Schedule of Assessments (Table 1).

The end of the study or study completion will be the last subject's last visit for any protocol-related activity.

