7.4 Early Termination

If a subject withdraws or is terminated from study treatment prior to completion of all study periods, all data collected at Visit 8 (Day 113) should be collected at the time of early termination. The subject will be asked to return to the study site 4 weeks after the last dose of study drug to complete the follow-up visit assessments (those performed on Day 141) as indicated in the Schedule of Assessments ([Table 1](#)).

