## 4. Study Details/Design

### 4.1. Brief Description

This multi-center, randomized, double-blind, placebo-controlled, parallel group, Phase 2a study is designed to assess the efficacy and safety of ME3183 administered orally in subjects with moderate to severe plaque psoriasis. The study consists of a 4-week Screening Period (Day -28 to Day -1), a 16-week double-blind Treatment Period (Day 1 to Day 113), and a 4-week Follow-up Period (Day 114 to Day 141). The total duration of study participation for each subject is approximately 24 weeks.

[figure not shown]
Note: The study drug is administered from Day 1 to Day 112 in the Treatment Period and the end of Treatment Period assessments will be performed on Day 113.

The duration of the Follow-up Period is from Day 114 to Day 141 and the end of Follow-up Period assessments will be performed on Day 141.

A suitable number of subjects with moderate to severe plaque psoriasis will be screened to randomize approximately 125 subjects across approximately 30 study sites in the United States and Canada. Subjects will be centrally randomized (25 subjects per treatment group) in a 1:1:1:1:1 ratio to 1 of the following treatment groups to receive oral ME3183 or matching placebo for a duration of 16 weeks.

- Treatment Group 1: [REDACTED] mg ME3183 BID administered orally: [REDACTED] capsule of [REDACTED] mg ME3183 and [REDACTED] capsules of matching placebo in the morning and evening
- Treatment Group 2: [REDACTED] mg ME3183 QD administered orally: [REDACTED] capsules of [REDACTED] mg ME3183 and [REDACTED] capsule of matching placebo in the morning and [REDACTED] capsules of matching placebo in the evening
- Treatment Group 3: [REDACTED] mg ME3183 BID administered orally: [REDACTED] capsule of [REDACTED] mg ME3183 and [REDACTED] capsule of [REDACTED] mg ME3183 and [REDACTED] capsule of matching placebo in the morning and evening
- Treatment Group 4: [REDACTED] mg ME3183 QD administered orally: [REDACTED] capsules of [REDACTED] mg ME3183 in the morning and [REDACTED] capsules of matching placebo in the evening
- Treatment Group 5: Matching placebo BID administered orally: [REDACTED] capsules of matching placebo in the morning and evening

This document is confidential.

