**Table 1. Schedule of Assessments**

Study Procedures	Screening Period	Treatment Period							Follow-up Period b
		Visit 2	Visit 3	Visit 4	Visit 5	Visit 6	Visit 7	Visit 8 a	
	Screening (Visit 1)	Visit 2	Visit 3	Visit 4	Visit 5	Visit 6	Visit 7	Visit 8 a	Follow-up Visit (Visit 9)
	Week -4	Week 0	Week 1	Week 2	Week 4	Week 8	Week 12	Week 16	Week 20
	Days -28 to -1	Day 1 (Baseline)	Day 8 (±1 day)	Day 15 (±1 day)	Day 29 (±3 days)	Day 57 (±3 days)	Day 85 (±3 days)	Day 113* (±3 days)	Day 141** (±3 days)
Eligibility Assessments									
Informed consent	X	-	-	-	-	-	-	-	-
Inclusion/exclusion criteria	X	X	-	-	-	-	-	-	-
Demographics	X	-	-	-	-	-	-	-	-
Dermatologic and medical history c	X	-	-	-	-	-	-	-	-
Prior and concomitant medications/therapies and procedures	X	X	X	X	X	X	X	X	X
History of previous treatment with a biologic drug for psoriasis	-	X	-	-	-	-	-	-	-
C-SSRS	X	X	-	-	-	-	-	-	-
Safety Assessments									
Physical examination (complete)	X	-	-	-	-	-	-	-	-
Physical examination (targeted)	-	X	X	X	X	X	X	X	X
Height and weight d	X	-	-	-	-	-	-	-	-
blood pressure (systolic and diastolic), heart rate, respiratory rate, body temperature, and body weight	X	X	X	X	X	X	X	X	X
12-lead ECGs e	X	X	-	-	X	X	X	X	X

This document is confidential.

Study Procedures	Screening Period	Treatment Period							Follow-up Period b
		Visit 2	Visit 3	Visit 4	Visit 5	Visit 6	Visit 7	Visit 8 a	
	Screening (Visit 1)	Visit 2	Visit 3	Visit 4	Visit 5	Visit 6	Visit 7	Visit 8 a	Follow-up Visit (Visit 9)
	Week -4	Week 0	Week 1	Week 2	Week 4	Week 8	Week 12	Week 16	Week 20
	Days -28 to -1	Day 1 (Baseline)	Day 8 (±1 day)	Day 15 (±1 day)	Day 29 (±3 days)	Day 57 (±3 days)	Day 85 (±3 days)	Day 113* (±3 days)	Day 141** (±3 days)
Safety Laboratory Tests									
Viral serology g	X	-	-	-	-	-	-	-	-
Hematology and Coagulation h	X	X i	X	X	X	X	X	X	X
Blood chemistry j	X	X i	X	X	X	X	X	X	X
Urinalysis	X	X	X	X	X	X	X	X	X
Pregnancy test (serum β-hCG) (WOCBP only)	X k	-	-	-	-	-	-	-	-
Pregnancy test (urine β-hCG) (WOCBP only)	-	X l, m	-	-	X m	X m	X m	X m	X m
Serum FSH (postmenopausal women only)	X	-	-	-	-	-	-	-	-
AE Monitoring									
Monitor for AEs and SAEs	X	X	X	X	X	X	X	X	X
Pharmacokinetic Assessments									
PK sample (blood) n	-	-	X	-	X	X	-	X	-

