Efficacy Assessments									
PASI score	X	X o	X	X	X	X	X	X	X
BSA	X	X o	X	X	X	X	X	X	X
sPGA	X	X o	X	X	X	X	X	X	X
PRO assessments	Itch NRS	-	X	X	X	X	X	X	X
	DLQI	-	X	X	X	X	X	X	X
CCI									
Other Assessments									

This document is confidential.

Study Procedures	Screening Period	Treatment Period							Follow-up Period b
		Visit 2	Visit 3	Visit 4	Visit 5	Visit 6	Visit 7	Visit 8 a	
	Screening (Visit 1)	Visit 2	Visit 3	Visit 4	Visit 5	Visit 6	Visit 7	Visit 8 a	Follow-up Visit (Visit 9)
	Week -4	Week 0	Week 1	Week 2	Week 4	Week 8	Week 12	Week 16	Week 20
	Days -28 to -1	Day 1 (Baseline)	Day 8 ( $\pm 1$ day)	Day 15 ( $\pm 1$ day)	Day 29 ( $\pm 3$ days)	Day 57 ( $\pm 3$ days)	Day 85 ( $\pm 3$ days)	Day 113* ( $\pm 3$ days)	Day 141** ( $\pm 3$ days)
Medical photography (target skin lesion) d	-	X	-	X	X	-	-	X	-
Clinical Drug Supplies									
Subject randomization	-	X	-	-	-	-	-	-	-
Dispense study drug	-	X	X	X	X	X	X	-	-
Administration of study drug g	-	X	X	X	X	X	X	-	-
Subject to return back unused study treatment for compliance check	-	-	X	X	X	X	X	X	-
Schedule the date/time for the next visit	X	X	X	X	X	X	X	X	-
Discharge the subject from the study site e	X	X	X	X	X	X	X	X	X

Abbreviations:  $\beta$ -hCG =  $\beta$ -human chorionic gonadotropin; AE = adverse event; BMI = body mass index; BSA = body surface area; C-SSRS = Columbia-Suicide Severity Rating Scale; DLQI = Dermatology Life Quality Index; ECG = electrocardiogram; FSH = follicle-stimulating hormone; HBV = hepatitis B virus; HCV = hepatitis C virus; PASI=Psoriasis Area and Severity Index; CCI [REDACTED]; PK=pharmacokinetic; PRO=patient-reported outcome; QTcF = QT interval corrected using Fridericia's formula; SAE = serious adverse event; sPGA = Static Physicians Global Assessment; WOCBP = women of childbearing potential; NRS = numerical rating scale.

\* The duration of the Treatment Period is from Day 1 to Day 112 and the end of Treatment Period assessments will be performed on Day 113.

\*\* The duration of the Follow-up Period is from Day 114 to Day 141 and the end of Follow-up Period assessments will be performed on Day 141.

a or Early Termination Visit.

b Subjects who discontinued or withdrew early from study treatment should return after 4 weeks of last dose of study treatment for follow-up safety assessments.

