#### **5.6. Safety Endpoints**

The safety endpoints are as follows:

- The incidence, severity, and seriousness of AEs reported over the 16-week Treatment Period and the 4-week Follow-up Period
- Changes from baseline in CS physical examination findings and vital sign measurements (blood pressure, heart rate, respiratory rate, body temperature, and body weight) over the 16-week Treatment Period and the 4-week Follow-up Period
- Changes from baseline in ECG findings over the 16-week Treatment Period and the 4-week Follow-up Period
- Changes from baseline in safety laboratory values (hematology, coagulation, blood chemistry, and urinalysis) over the 16-week Treatment Period and the 4-week Follow-up Period

This document is confidential.

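### SAP 2.2 ties lock and analysis to Visit 8 (Week 16) as the final visit, but both schedules end at Visit 9 (Week 20) and the safety endpoints run to it

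*SAP*

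**What the plan says.** SAP 2.2 (Timings of Analyses) sets one primary analysis, covering safety, efficacy and PK, to take place "after all subjects complete the final study visit (Visit 8 at Week 16) or terminate early from the study". It adds: "Database will be completely cleaned and locked prior to the primary analysis". It plans no interim analysis and describes no later lock or later safety analysis.

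The rest of the plan goes on past Visit 8:

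- **Schedule.** SAP 4.1 and Table 1, like Protocol 7.1 and Table 1, have a Follow-up Period from Day 114 to Day 141, and "the end of Follow-up Period assessments will be performed on Day 141". Table 1 calls this Visit 9, Week 20. AEs, vital signs, ECG, laboratory tests and a targeted physical examination are all scheduled there.
- **End of study.** Protocol 7.3 makes a subject's completion depend on the Follow-up Period, and ends the study at the last subject's "last visit for any protocol-related activity".
- **Safety endpoints.** SAP 5.6 lists "The incidence, severity, and seriousness of AEs reported over the 16-week Treatment Period and the 4-week Follow-up Period" and gives the same span for vital signs, ECG and laboratory values. The safety estimands in SAP 7.3 repeat it. SAP 13.1 collects AEs until 4 weeks after last dose, and SAP 13.1.4 has an onset category of Day 114+.
- **Early stoppers.** SAP Table 1, footnote b: "Subjects who discontinued or withdrew early from study treatment should return after 4 weeks of last dose of study treatment for follow-up safety assessments". Protocol 7.4 agrees: "The subject will be asked to return to the study site 4 weeks after the last dose of study drug".
- **Blinding.** SAP 4.4.2 and Protocol 9.3.2 keep sponsor staff and designees blinded for as long as the study lasts, apart from stated exceptions.

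**The concern.** The sentence that decides when the database is locked names the wrong visit as the last one. If it were followed literally, subjects still in follow-up at lock would lack their Week 20 safety assessments and any AE arising between lock and the end of their follow-up. The safety tables that SAP 5.6, 7.3 and 13.1.4 define through follow-up would then be incomplete for those subjects, and no later analysis is described that would complete them.

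There is a second conflict. The planned analysis compares treatment groups, so running it before the last Visit 9 would unblind people while the study, as Protocol 7.3 defines it, is still open.

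The early-termination branch is unclear too. SAP 2.2 speaks of terminating from the study, whereas the 4-week return visit applies to subjects who stop study treatment. Protocol 8.4 treats the two as different things. SAP 2.2 does not say whether lock waits for that return visit.

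**Working it through.** **Which visit is last.** Inputs are the nominal days and windows in Table 1 of either document.

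- Visit 8: (113 − 1)/7 = 16. The Week 16 label is correct.
- Visit 9: (141 − 1)/7 = 20. A later scheduled visit exists, so the description of Visit 8 as final does not hold.
- Nominal gap: 141 − 113 = 28 days.
- Shortest gap with ±3 days at each visit: (141 − 3) − (113 + 3) = 22 days.
- Longest gap: (141 + 3) − (113 − 3) = 34 days.

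**What depends on the interval.** The Day 114+ onset category lies wholly after the nominal Visit 8 day. The vital sign and ECG summaries in SAP 13.3 and 13.4 are specified for every scheduled visit, which includes Visit 9. The primary endpoint is read at Week 16, the secondary efficacy endpoints defined by visit stop at Week 16, and the last PK sample is at Week 16.

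**How many subjects could be outstanding.** The documents give N = 125 but no accrual period and no time from last visit to lock, so both must be assumed. With uniform accrual over A weeks, lock d days after the last Visit 8, and a gap of g days between visits:

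outstanding = 125 × max(0, g − d)/(7A)

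| Lock after last Visit 8 | A = 26 | A = 39 | A = 52 | A = 65 |
|---|---|---|---|---|
| d = 14, g = 28 | 9.6 | 6.4 | 4.8 | 3.8 |
| d = 14, g = 22 to 34 | 5.5 to 13.7 | 3.7 to 9.2 | 2.7 to 6.9 | 2.2 to 5.5 |
| d = 28, g = 28 | 0 | 0 | 0 | 0 |
| d = 28, g = 34 | 4.1 | 2.7 | 2.1 | 1.6 |
| d ≥ 34, any g | 0 | 0 | 0 | 0 |

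For the first cell: 125 × 14/(7 × 26) = 1750/182 = 9.6. The g = 34 rows need every subject at the extreme of both windows. The count varies inversely with A, so a shorter accrual gives larger figures and the formula sets no ceiling. Drop-out is ignored here.

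**The case against.** The strongest case on the other side is that this is a slip in a parenthesis and the rest of the plan corrects it. The word after gives only an earliest time. The database must be completely cleaned first (SAP 2.2), and the blind data review meeting comes before lock (SAP 9.2), so lock on the day of the last Visit 8 is not realistic. Blinding for the length of the study, together with the end-of-study definition in Protocol 7.3, points to unblinding after Visit 9. The outputs themselves need Week 20 data.

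Most of this stands, and it makes a mislabelled visit the likelier explanation. It does not repair the rule. Neither cleaning nor blind review is tied to Visit 9. Section 15 of the protocol lets the SAP prevail where the two differ, so Protocol 7.3 cannot be counted on to override SAP 2.2.

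A reader might infer more: that the sponsor plans to lock at Week 16 and will lose follow-up safety data for up to about 19 of 125 subjects. The documents do not support that. The figure is 125 × 28/(7 × 26) = 19.2, which needs both an assumed 26-week accrual and lock on the day of the last Visit 8, leaving no time for the cleaning and review that must come first. Nor is it a ceiling: a 34-day gap gives 23.4 under the same assumptions.

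**Conclusion.** SAP 2.2 is wrong as written. The final visit is Visit 9, nominally 28 days after Visit 8 (22 to 34 with the windows), and the stated trigger neither secures the follow-up safety data that the SAP promises to analyse nor fits the blinding text. It permits an early lock but does not show that one is intended.

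The number of subjects with Week 20 data outstanding cannot be bounded from the documents. It is 0 if lock is 34 or more days after the last Visit 8. About 10 of 125 is an illustration that rests on two assumptions: uniform accrual over 26 weeks and lock 2 weeks after the last Visit 8.

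The effect is confined to safety follow-up and blinding; Week 16 efficacy and PK data are untouched. Severity is minor to should-fix. Confidence is high for the mismatch of visits, and much lower for any actual loss of data.

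**What to change.** Change SAP 2.2 so that database lock, release of treatment codes and analysis all follow after every subject has completed Visit 9 (Week 20) or, if they stopped early, has completed the follow-up visit 4 weeks after last dose, withdrawn from the study or been lost to follow-up. The blinding exceptions already in SAP 4.4.2 can stay. The new wording also settles the early-termination branch.

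The cost is one sentence. The read-out comes at most about 4 weeks (22 to 34 days) later than the earliest time the present text allows, and no later at all if cleaning and blind review take that long anyway.

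A separate Week 16 read-out is not a simple alternative. It would conflict with the statement in SAP 2.2 that no interim analyses are planned and with study-long blinding in both documents, so those passages, including the protocol's, would have to change as well.
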